### 5.6.6 Other Safety Analyses

The results of C-SSRS assessments will be listed for each subject. The incidence of suicidal ideation or suicidal behavior may be summarized by treatment group as appropriate.

## 5.7 Other Analyses

Not applicable.

## 6 INTERIM ANALYSES

No formal interim analyses are planned for this study.

## 7 CHANGES IN THE PLANNED ANALYSES

There are no changes to the statistical methods in this analysis plan compared to the latest protocol. However, there is no data with 10 mg thus the statistical analyses and TLGs do not include 10 mg.

## 8 DEFINITIONS AND CONVENTIONS FOR DATA HANDLING

### 8.1 Definitions of Baseline Values

For PPR analyses in all treatment periods, the predose PPR data from the respective treatment period will be used as baseline data for that period. If predose PPR data is not valid, the average PPR value at screening visit will be used as baseline for PPR analyses.

The baseline value for all safety endpoints will be the last non-missing measurement occurring prior to the first dose of study drug in the treatment period 1.

### 8.2 Definitions of Treatment Periods

Treatment periods 1 to 4 are one-day treatment periods which will include single dose of study drug on Day 1 (Visit 2) for treatment period 1, Day 15 (Visit 3) for treatment period 2, Day 29 (Visit 4) for treatment period 3, and Day 43 (Visit 5) for treatment period 4.

### 8.3 Definitions of Derived PPR Variables

The followings are definitions for PPR related analyses:

- Standard Photosensitivity Response (SPR): a standardized derived measure of the range of frequencies of IPS that elicits epileptiform EEG responses in a subject. The range is assigned a number, representing the number of frequency steps, from 0 to 14 between the lowest to the highest frequencies of IPS that elicits epileptiform activity by EEG. If the upper and lower limit of measured frequencies is the same, SPR will be set = 1.

- Most sensitive eye condition: SPR is measured in each of 3 eye states: eye closure, eyes closed, and eyes open. That eye condition that yields the largest SPR before dosing is defined as the most sensitive eye condition.
- Duration of suppression: The difference in hours between the onset of suppression and the end of suppression of photosensitivity. The onset of suppression is defined as the first time point at which the SPR was at least 3 units below the mean SPR at baseline. The end of suppression is defined as the last time (second time) with two successive reductions in SPR of at least 3 units lower than the mean SPR at baseline.
- Response: Complete suppression is defined as a standardized photosensitivity response (SPR) reduction to 0 over at least 1 time point for all three eye conditions. Partial response is defined as a reduction in SPR of at least 3 units from baseline for at least 3 time points, and no time points with at least 3 units of increase, in the most sensitive eye condition; without meeting the complete suppression definition. No response is defined as the response not meeting complete suppression or partial suppression definitions.

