### 9.3.1 Inclusion Criteria

Subjects must meet all of the following criteria to be included in this study:

1. Male or female 18 to 65 years of age at the time of informed consent.
2. A diagnosis and/or history of a PPR on EEG (ie, photosensitivity epilepsy).
3. If currently being treated with AED(s), up to a maximum of 3 concomitant AEDs is allowed provided that doses must have remained stable for at least 4 weeks or 5 half-lives, whichever longer, before Screening. In the case where a new AED regimen has been initiated for a subject, the subject must be on the new AED for at least 8 weeks before Screening and the dose must have remained stable for at least 4 weeks or 5 half-lives, whichever is longer, before Screening. (See [Exclusion Criteria No. 17-22](#) for AEDs that are exclusionary). (revised per Amendment 01)
4. Reproducible IPS-induced PPR on EEG of at least 3 points on the SPR scale in at least 1 eye condition (eye closure, eyes closed, eyes open) on at least 3 of the EEGs performed at Screening.
5. Body mass index (BMI) between 18 to 35 kg/m^2 (inclusive) and a total body weight greater than or equal to 45 kg at Screening.
6. Agrees to refrain from strenuous exercise and alcohol consumption during the 24-hour period before Screening and during the 24-hour period before each treatment day.
7. Willing and able to comply with all aspects of the protocol.

Note: Subjects who have completed the study per original protocol may re-enter the study provided that the subject meet inclusion criteria No. 2 to 7. (revised per Amendment 01)

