## 9.7 Statistical Methods

All statistical analyses will be performed by the sponsor or designee after the study is completed and the database is locked and released for unblinding. Statistical analyses will be performed using SAS software or other validated statistical software as required. Data will be unblinded once double-blind treatment period has completed. Two sets of analyses tables will be created: one set after the unblinding using all the available data until that point and another set after all the subjects have completed the last study visit.

Descriptive statistics will be presented including mean and standard deviation of photosensitivity range for each subject at Screening and at each time point, for each Treatment Visit day by treatment group. Graphical displays of the data for each subject will allow exploration of intersubject and intrasubject variability. Details of statistical methods and analyses will be included in a separate statistical analysis plan (SAP).

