#### 4 DETERMINATION OF SAMPLE SIZE

Based on a similar study in subjects with photosensitive epilepsy (NCT02564029), an estimated standard deviation of the treatment group difference of the SPR in the subject’s most sensitive eye condition is 3.62. The width of a 90% CI of the mean group difference based on this standard deviation assumption and 6 subjects is 2.431. Therefore, a sample size of 6 would be sufficient to detect a mean group difference of 3 or larger with 90% confidence.

Approximately 9 subjects with photosensitive epilepsy and a stable PPR will be needed to be randomized in the study in order to obtain 6 evaluable subjects.

A subject will be defined as evaluable if the subject has completed at least 2 treatment periods (including one with placebo) and has more than 50% non-missing postdose PPR data in each period to get the average PPR value (i.e., at least 3 of 5 posedose PPR data are valid in each period).

Subjects who discontinue from the study early may be replaced after consultation with the sponsor.

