#### 5.1.2 Secondary Endpoints

- Mean change from baseline in the PPR range in each of the 3 eye conditions (eye closure, eyes closed, and eyes open) at each dose level of E2082 compared to placebo
- Onset, maximum change, and duration of response in each of the 3 eye conditions (eye closure, eyes closed, and eyes open) at each dose level of E2082
- Frequency and percentage of subjects with complete suppression, partial response, and no response of SPR at each dose level of E2082
- Changes from baseline in BL-VAS at each dose level of E2082
- Incidence of TEAEs at each dose level of E2082
- Clinically significant changes from baseline in vital signs, serum chemistries, complete blood counts, or liver function tests after single doses of E2082, compared to placebo
- PK parameters of E2082 ( $C_{max}$ ,  $t_{max}$ , area under concentration-time curve from time 0 to 8 hours postdose [ $AUC_{(0-8h)}$ ])
- Relationship between PK parameters of E2082 onset, maximum change, and duration of impact on photosensitivity

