#### 5.3.5 Handling of Missing Data, Dropouts, and Outliers

Missing values in PPR will not be imputed in this study.

For PD analyses, two summaries for the primary and secondary PPR endpoints will be produced, if different, one for all data in PD analysis set and one for all completers.

For safety summaries, all data in Safety Analysis Set will be included.

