#### Secondary PD Analyses

The secondary endpoints of mean change from baseline of the average PPR for each E2082 dose for all 3 different eye conditions (eye closure, eyes closed, and eyes open) will be summarized by treatment group and compared with placebo by using the same mixed effects model as for primary PD analyses.

Table and figure for the proportions of subjects with complete suppression, partial response, or no response will be displayed by treatment group (see [section 8.3](#) for definition of complete, partial suppression or no response).

Evaluation of onset, maximum change, and duration of photosensitivity response at each dose level will be performed for all 3 eye conditions for each treatment using summary and graphical displays.

Sensitivity analyses may be conducted for photosensitivity response, for example, in subjects who completed all 3 Treatment Periods 1 through 3 versus those who are included in the PD Analysis Set. Other exploratory analyses may be conducted as data permit.

All other PD data (ie, BL-VAS data) may be summarized by treatment groups using standard summary statistics.

PK-PD analyses may include examination of relationship between PK of E2082 and SPR (eg, time of onset, maximum change, and duration of response; and BL-VAS data) using model-based approaches as permitted by data. Details of the PK/PD analyses will be described in a separately prepared analysis plan and its report.

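### SAP 8.3 starts duration of suppression on one reduced reading but ends it on two successive ones, so some responses get no duration, some span unsuppressed readings, and suppression still present at 8 h is truncated

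*SAP*

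**What the plan says.** SAP 8.3 defines duration as the hours between onset and end of suppression.

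- **Onset:** "The onset of suppression is defined as the first time point at which the SPR was at least 3 units below" baseline. One reading is enough.
- **End:** "The end of suppression is defined as the last time (second time) with two successive reductions in SPR of at least 3 units" below baseline. Two readings in a row are needed.

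SAP 5.1.2 makes this a secondary endpoint: "Onset, maximum change, and duration of response in each of the 3 eye conditions", at each dose level. SAP 5.5.2 adds: "Evaluation of onset, maximum change, and duration of photosensitivity response at each dose level will be performed for all 3 eye conditions", by summary and graphical displays. No test or confidence interval is planned for it.

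Protocol 9.1.2.1 sets the postdose readings at 1, 2, 4, 6 and 8 h. SAP 5.3.5 says "Missing values in PPR will not be imputed in this study". SAP section 4 counts a period as evaluable if "at least 3 of 5 posedose PPR data are valid in each period", so up to two readings may be absent. SAP 8.3 gives no value for an onset without a later pair, no rule for suppression still present at 8 h, and no statement on whether readings either side of a missing one are successive. SAP section 9 leaves programming rules to separate documents that are not part of the package.

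**The concern.** Because the two ends of the interval use different criteria, the stated rule can fail in three ways. A subject can have an onset and no end. An isolated early reduction can be joined to a much later pair, so that the unsuppressed readings between them count as suppressed time. And when the last pair is 6 and 8 h, the end is set at 8 h although nothing was observed afterwards.

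The study is meant to show a dose-response relationship and to inform dose selection (Protocol 7.2.1). If suppression often outlasts 8 h, an 8 h ceiling compresses the durations and could blunt differences between doses. With 6 evaluable subjects planned, one absent or misleading value can shift a descriptive summary. The effect is confined to duration; the average-PPR analyses do not use it.

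**Working it through.** The documents give no figure for this derivation, so there is none to reproduce. The check lists every possible outcome of the rule.

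**Inputs.** Reading times 1, 2, 4, 6 and 8 h (Protocol 9.1.2.1). Each reading is either reduced (at least 3 units below baseline) or not (SAP 8.3). Braces list the reduced times.

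**Rule as coded.** Onset = first reduced reading. End = second reading of the last adjacent reduced pair. Duration = end − onset.

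**Step 1: patterns with an onset.** 2^5 − 1 = 31.

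**Step 2: onset but no pair.** Of the 32 on/off strings of length 5, 13 have no two adjacent reductions. Removing the empty one leaves 13 − 1 = 12: {1}, {2}, {4}, {6}, {8}, {1,4}, {1,6}, {1,8}, {2,6}, {2,8}, {4,8}, {1,4,8}. None has a duration. {1,4,8} has three reduced time points, which need not be successive for a partial response under the same section. In the most sensitive eye condition it can therefore be a partial response (if SPR does not rise by 3 units at 2 or 6 h) with no duration.

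**Step 3: the other 31 − 12 = 19 patterns.**

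Five span unsuppressed readings:

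| Pattern | Duration as written | Longest unbroken run |
|---|---|---|
| {2,6,8} | 8 − 2 = 6 h | 2 h |
| {1,6,8} | 8 − 1 = 7 h | 2 h |
| {1,4,6} | 6 − 1 = 5 h | 2 h |
| {1,4,6,8} | 8 − 1 = 7 h | 4 h |
| {1,2,6,8} | 8 − 1 = 7 h | 2 h |

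Suppression at all five readings also scores 8 − 1 = 7 h.

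Eight end at 8 h: {6,8}, {4,6,8}, {2,6,8}, {2,4,6,8}, {1,6,8}, {1,4,6,8}, {1,2,6,8} and all five. Four of these are also in the table, so 5 + 8 − 4 = 9 patterns have one or both problems. Four more, {1,2,6}, {1,2,8}, {2,4,8} and {1,2,4,8}, leave a later isolated reduction outside the interval. That leaves 19 − 9 − 4 = 6 with none of these features.

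**Step 4: missing readings.** With one or two of five readings missing and at least one reduction there are 75 + 70 = 145 patterns. In 8 + 12 = 20 the result depends on whether succession bridges the gap, and in 14 of those a duration exists only if it does. Example: reductions at 1 and 4 h with 2 h missing give 4 − 1 = 3 h, or no value.

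**Step 5: the recommended rule** (onset for duration = first reading of the first pair; end unchanged). The same 12 patterns form one stated category. {2,6,8}, {1,6,8} and {1,4,6} become 2 h and {1,4,6,8} becomes 4 h, so only {1,2,6,8} still spans an unsuppressed reading. The 8 patterns ending at 8 h become censored and 19 − 8 = 11 stay exact. Reductions outside the counted interval rise from 4 to 8 of 19, because the four early isolated ones are no longer counted.

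**The case against.** The strongest reply is that this is a clumsy sentence about one descriptive variable. Several parts of that reply stand.

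- The parenthesis in the end rule might suggest that the end is the second reading of the first pair, so that suppression at all five readings could score 1 h instead of 7 h. The text does not support that reading, because it gives the word 'last' no meaning. The last-pair reading is the natural one and is used here.
- A reader might take 12 of 31 as a forecast that about four in ten subjects have no duration. It is not; every pattern is weighted equally. Of the 15 unbroken-run patterns 5 lack a duration, and all 5 are single reductions. Requiring a confirmed pair may be deliberate.
- A reader might also infer that an 8 h end will be averaged as an exact value. The SAP does not say so; it only sets the end there. Protocol 9.7 plans descriptive statistics of the "photosensitivity range for each subject at Screening and at each time point, for each Treatment Visit day by treatment group" and graphs for each subject, so status at 8 h is partly visible.
- The 3-of-5 condition was written for the average PPR, not for duration, and 125 of the 145 missing-data patterns do not depend on bridging.
- The separate programming documents may settle some of this. They cannot be checked here.

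What does not fall away: on the natural reading, the endpoint definition itself returns no value for a possible partial responder, equates {1,6,8} with continuous suppression, and fixes an unobserved end at 8 h. That belongs in the SAP, not in a programmer's choice.

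**Conclusion.** The point holds, at the level of a change that should be made to a descriptive secondary endpoint. On the last-pair reading with complete data, 12 of 31 patterns have an onset but no duration, 5 span unsuppressed readings, 8 end at the 8 h limit (4 of these also span), and 6 have none of the problems listed.

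How often each pattern will occur cannot be derived from the documents. That suppression may last beyond 8 h is plausible: Protocol 7.1.2.1 gives a half-life of about 30 h, and Protocol 9.4.4 expects even 2.5 mg to hold the predicted minimum effective concentration for about 8 h. That a 3-unit SPR fall follows concentration is an assumption.

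Two larger conclusions are not supported. The primary analysis is unaffected, since it uses the average of the postdose readings. And duration need not be redefined as the longest unbroken run; that is a matter of preference.

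**What to change.** Amend SAP 8.3 only, before unblinding:

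1. State that the end is the second reading of the last successive pair.
2. Use the same two-successive-reading criterion for the onset that enters duration, taking the first reading of the first pair. Keep the separately reported first-reduction onset as it is. Report subjects with reductions but no pair as 'no sustained suppression', with n (%), so that they are neither dropped nor given an arbitrary value.
3. If the end is at 8 h, report duration as '>= x h' (censored) and do not average it as exact. Report n (%) suppressed at 8 h by treatment and eye condition.
4. State that a missing reading breaks succession, and flag affected values.
5. Flag any duration that spans an unsuppressed reading.

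The cost is SAP wording and minor programming, with no new assessments. Duration becomes slightly less simple to summarise, and the first-reduction onset can precede the onset used for duration: for {1,4,6} these are 1 h and 4 h. Isolated reductions outside the counted interval stay visible through the first-reduction onset, the per-time-point summaries and the 8 h count.

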#### **8.4 Definitions of PK Data Handling**

Rules for handling PK data for derivation of PK parameters will be defined in separate PK report. When presenting individual/raw values and summary statistics, the following rule will be applied: for drug concentrations and all summary statistics will have 3 significant digits except for tmax will have 2 decimal places.

### **9 PROGRAMMING SPECIFICATIONS**

The rules for programming derivations and dataset specifications will be provided in separate documents.

### **10 STATISTICAL SOFTWARE**

All statistical analyses will be performed using SAS v 9.3 or later.

### **11 MOCK TABLES, LISTINGS, AND GRAPHS**

The study TLG shells will be provided in a separate document, which will show the content and format of all tables, listings, and graphs in detail.

### 13 APPENDICES

#### 13.1 Sponsor’s Grading for Laboratory Values

**Sponsor’s Grading for Laboratory Values**

	Grade 1	Grade 2	Grade 3	Grade 4
BLOOD/BONE MARROW				
Hemoglobin	<LLN – 10.0 g/dL <LLN – 100 g/L <LLN – 6.2 mmol/L	<10.0 – 8.0 g/dL <100 – 80 g/L <6.2 – 4.9 mmol/L	<8.0 g/dL <80 g/L <4.9 mmol/L; transfusion indicated	life-threatening consequences; urgent intervention indicated
Leukocytes (total WBC)	<LLN – 3.0×10  /L <LLN – 3000/mm 	<3.0 – 2.0×10  /L <3000 – 2000/mm 	<2.0 – 1.0×10  /L <2000 – 1000/mm 	<1.0×10  /L <1000/mm 
Lymphocytes	<LLN – 800/mm  <LLN – 0.8×10  /L	<800 – 500/mm  <0.8 – 0.5×10  /L	<500 – 200/mm  <0.5 – 0.2×10  /L	<200/mm  <0.2×10  /L
Neutrophils	<LLN – 1.5×10  /L <LLN – 1500/mm 	<1.5 – 1.0×10  /L <1500 – 1000/mm 	<1.0 – 0.5×10  /L <1000 – 500/mm 	<0.5×10  /L <500/mm 
Platelets	<LLN – 75.0×10  /L <LLN – 75,000/mm 	<75.0 – 50.0×10  /L <75,000 – 50,000/mm 	<50.0 – 25.0×10  /L <50,000 – 25,000/mm 	<25.0×10  /L <25,000/mm 
METABOLIC/LABORATORY				
Albumin, serum- low (hypoalbuminemia)	<LLN – 3 g/dL <LLN – 30 g/L	<3 – 2 g/dL <30 – 20 g/L	<2 g/dL <20 g/L	life-threatening consequences; urgent intervention indicated
Alkaline phosphatase	>ULN – 3.0×ULN	>3.0 – 5.0×ULN	>5.0 – 20.0×ULN	>20.0×ULN
ALT	>ULN – 3.0×ULN	>3.0 – 5.0×ULN	>5.0 – 20.0×ULN	>20.0×ULN
AST	>ULN – 3.0×ULN	>3.0 – 5.0×ULN	>5.0 – 20.0×ULN	>20.0×ULN
Bilirubin (hyperbilirubinemia)	>ULN – 1.5×ULN	>1.5 – 3.0×ULN	>3.0 – 10.0×ULN	>10.0×ULN
Calcium, serum-low (hypocalcemia)	<LLN – 8.0 mg/dL <LLN – 2.0 mmol/L	<8.0 – 7.0 mg/dL <2.0 – 1.75 mmol/L	<7.0 – 6.0 mg/dL <1.75 – 1.5 mmol/L	<6.0 mg/dL <1.5 mmol/L
Calcium, serum-high (hypercalcemia)	>ULN – 11.5 mg/dL >ULN – 2.9 mmol/L	>11.5 – 12.5 mg/dL >2.9 – 3.1 mmol/L	>12.5 – 13.5 mg/dL >3.1 – 3.4 mmol/L	>13.5 mg/dL >3.4 mmol/L
Cholesterol, serum-high (hypercholesterolemia)	>ULN – 300 mg/dL >ULN – 7.75 mmol/L	>300 – 400 mg/dL >7.75 – 10.34 mmol/L	>400 – 500 mg/dL >10.34 – 12.92 mmol/L	>500 mg/dL >12.92 mmol/L
Creatinine	>ULN – 1.5×ULN	>1.5 – 3.0×ULN	>3.0 – 6.0×ULN	>6.0×ULN
GGT (γ-glutamyl transpeptidase)	>ULN – 3.0×ULN	>3.0 – 5.0×ULN	>5.0 – 20.0×ULN	>20.0×ULN
Glucose, serum-high (hyperglycemia)	Fasting glucose value: >ULN – 160 mg/dL >ULN – 8.9 mmol/L	Fasting glucose value: >160 – 250 mg/dL >8.9 – 13.9 mmol/L	>250 – 500 mg/dL; >13.9 – 27.8 mmol/L; hospitalization indicated	>500 mg/dL; >27.8 mmol/L; life-threatening consequences
Glucose, serum-low (hypoglycemia)	<LLN – 55 mg/dL <LLN – 3.0 mmol/L	<55 – 40 mg/dL <3.0 – 2.2 mmol/L	<40 – 30 mg/dL <2.2 – 1.7 mmol/L	<30 mg/dL <1.7 mmol/L

### Sponsor's Grading for Laboratory Values

	Grade 1	Grade 2	Grade 3	Grade 4
				life-threatening consequences; seizures
Phosphate, serum-low (hypophosphatemia)	<LLN – 2.5 mg/dL <LLN – 0.8 mmol/L	<2.5 – 2.0 mg/dL <0.8 – 0.6 mmol/L	<2.0 – 1.0 mg/dL <0.6 – 0.3 mmol/L	<1.0 mg/dL <0.3 mmol/L life-threatening consequences
Potassium, serum-high (hyperkalemia)	>ULN – 5.5 mmol/L	>5.5 – 6.0 mmol/L	>6.0 – 7.0 mmol/L hospitalization indicated	>7.0 mmol/L life-threatening consequences
Potassium, serum-low (hypokalemia)	<LLN – 3.0 mmol/L	<LLN – 3.0 mmol/L; symptomatic; intervention indicated	<3.0 – 2.5 mmol/L hospitalization indicated	<2.5 mmol/L life-threatening consequences
Sodium, serum-high (hypernatremia)	>ULN – 150 mmol/L	>150 – 155 mmol/L	>155 – 160 mmol/L hospitalization indicated	>160 mmol/L life-threatening consequences
Sodium, serum-low (hyponatremia)	<LLN – 130 mmol/L	N/A	<130 – 120 mmol/L	<120 mmol/L life-threatening consequences
Triglyceride, serum-high (hypertriglyceridemia)	150 – 300 mg/dL 1.71 – 3.42 mmol/L	>300 – 500 mg/dL >3.42 – 5.7 mmol/L	>500 – 1000 mg/dL >5.7 – 11.4 mmol/L	>1000 mg/dL >11.4 mmol/L life-threatening consequences
Uric acid, serum-high (hyperuricemia)	>ULN – 10 mg/dL ≤0.59 mmol/L without physiologic consequences	N/A	>ULN – 10 mg/dL ≤0.59 mmol/L with physiologic consequences	>10 mg/dL >0.59 mmol/L life-threatening consequences

ALT = alanine aminotransferase (serum glutamic pyruvic transaminase), AST = aspartate aminotransferase (serum glutamic oxaloacetic transaminase), GGT =  $\gamma$ -glutamyl transpeptidase, N/A = not applicable, LLN = lower limit of normal, ULN = upper limit of normal, WBC = white blood cell.

Based on Common Terminology Criteria for Adverse events (CTCAE) Version 4.0. Published: May 28, 2009 (v4.03: June 14, 2010).

## 13.2 SAS Code of Mixed Model for Primary PD Analyses

```
proc mixed data= xxx;
  class USUBJID TRTPN PERIOD SEQUENCE ;
  model AVAL = TRTPN PERIOD SEQUENCE BASE /SOLUTION ddfm= kr;
  random USUBJID(SEQUENCE) ;
  lsmeans TRTPN/alpha= 0.1 PDIFF CL
  pdiff=control('Placebo') ;
run;
```

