### 5.1 Study Endpoints

#### 5.1.1 Primary Endpoint

The primary endpoint is mean change from baseline in the PPR range in each subject's most sensitive eye condition at each dose level of E2082 as compared to placebo.

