### 5.5.2 Pharmacodynamic Analyses

No multiplicity adjustments will be made. The PPR measurements collected at the 5 postdose timepoints on a given treatment day will be averaged and the arithmetic average value will be used for both primary endpoint and secondary endpoint analyses. The predose PPR data from the respective treatment period will be used as the baseline data for that period. The following PD analyses will be performed on the PD Analysis Set.

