#### Primary PD Analyses

The reduction in PPR response will be evaluated for 8 hours postdose during each Treatment Period. A diminution in response is anticipated with the dose range.

The primary endpoint, mean change from baseline of the average PPR in the most sensitive eye condition, will be summarized by treatment group, and analyzed using a mixed effects model for crossover part of the study. The mixed effects model for the crossover part of the study will include treatment (E2082 2.5 mg, 25 mg, and placebo), period, and sequence as fixed effects, baseline (predose) measurement as a covariate, and subject nested within sequence as a random effect. Least squares (LS) means, difference in LS means of each E2082 dose (2.5 mg or 25 mg) compared to placebo, and 90% CIs will be presented with no adjustments for multiplicity.

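### Does the undefined AVAL, or SEQUENCE in a very small fit, in the SAP 13.2 code put the primary analysis at risk?

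*SAP*

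**What the plan says.** SAP 5.5.2, under Primary PD Analyses, names the primary variable: "mean change from baseline of the average PPR in the most sensitive eye condition, will be summarized by treatment group, and analyzed using". The method it then gives is a mixed model with treatment, period and sequence as fixed effects, baseline as covariate and subject within sequence as random effect. Its outputs are "Least squares (LS) means, difference in LS means of each E2082 dose (2.5 mg or 25 mg) compared to placebo, and 90% CIs". SAP 5.1.1 states the endpoint as change "at each dose level of E2082 as compared to placebo".

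The opening paragraph of 5.5.2 averages the five postdose values of a treatment day and says that "the arithmetic average value will be used for both primary endpoint and secondary endpoint analyses". The code in SAP 13.2 is "model AVAL = TRTPN PERIOD SEQUENCE BASE /SOLUTION ddfm= kr", with a random term for subject within sequence and LS means at alpha 0.1. AVAL is not defined. SAP 9 leaves derivation rules and dataset specifications to other documents, and SAP 11 does the same for the table shells.

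BASE is settled by SAP 8.1: the predose value of the same period, with one fallback, "If predose PPR data is not valid, the average PPR value at screening visit will be used as baseline for PPR analyses".

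On numbers, SAP 4 randomizes about 9 subjects "in order to obtain 6 evaluable subjects" over six sequences. The model is run on the PD Analysis Set, which takes in any randomized, dosed subject with at least one derivable PD parameter. SAP 5.3.5 plans two summaries of the PPR endpoints, "one for all data in PD analysis set and one for all completers", without saying that the mixed model is refitted for the second. The secondary section of 5.5.2 makes a completer sensitivity analysis optional.

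**The concern.** Two things look wrong on a first reading of the code.

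First, text and code do not visibly name the same outcome. Because 5.5.2 says the postdose average is what enters the analyses, AVAL can be taken to be that average. The LS means would then be photosensitivity levels at mean baseline in a table whose text promises changes. A reader could take a printed 5 for a worsening of 5 steps when it is a postdose level.

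Second, the design has six sequences and a target of six evaluable subjects. With one subject in each sequence, knowing the sequence is the same as knowing the subject. The fixed SEQUENCE effect then takes up all between-subject variation, the random subject variance cannot be estimated, and the SAP has no rule for that case. If the software reports the variance as zero, the CIs of the individual LS means carry within-subject error only.

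At stake would be the scale and the CIs of the LS means. The question is whether anything reaches the dose-placebo comparison.

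**Working it through.** **Inputs.** SD of the treatment difference 3.62, six sequences, about 9 randomized and 6 evaluable (SAP 4 and 3.2); 90% two-sided CIs (SAP 13.2). The plan's own figure reproduces from that SD: 1.645 × 3.62/√6 = 2.431. (This is a half-width, although SAP 4 calls it a width; that is a separate matter.) The within-subject SD follows as 3.62/√2 = 2.56, variance 6.55. Between-subject SD is not in the documents and is varied as an assumption.

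**Response variable.** Write the model for the postdose average as

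AVAL = Xβ + γ·BASE + subject + error.

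Subtract BASE from both sides:

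CHG = Xβ + (γ − 1)·BASE + subject + error.

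β, the residuals, the variance components and the degrees of freedom are the same. Only the BASE slope changes, by exactly 1. At mean baseline m, an LS mean is xβ + γm for AVAL and xβ + (γ − 1)m for CHG, so each shifts by m and the shift cancels from every difference. The SEs of the LS means are also equal. In a numerical check the treatment coefficients agreed, the BASE slope differed by 1, and each LS mean moved by the mean BASE of that dataset (7.717).

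The identity requires CHG to use the same BASE as the covariate. In 200 simulated 9-subject trials with one predose value replaced by the screening average, as SAP 8.1 directs, AVAL and CHG gave differences and SEs equal to within 1e-9. A change built on predose alone would lose that row and move the differences by a median of 0.13 to 0.17 steps, but SAP 8.1 already rules that construction out.

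**Aliasing.** The fixed-effect columns have rank 1 + 2 + 2 + 5 + 1 = 11 (intercept, treatment, period, sequence, BASE).

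| Layout | Rank, fixed effects | Rank, subject columns added | df for subject variance |
|---|---|---|---|
| 6 subjects, one per sequence | 11 | 11 | 0 |
| 7 subjects over 6 sequences | 11 | 12 | 1 |
| 9 subjects over 6 sequences | 11 | 14 | 3 |

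At 0 df the REML log-likelihood is flat in the subject variance (−16.543737 at 0, 1, 4, 9 and 25). If the variance is then taken as 0, the LS-mean CI is built on 6.55/6, while the sampling variance of the LS mean is (6.55 + SDb²)/6. Ignoring the covariate's contribution to the variance, coverage is

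P(|t₇| < 1.895/√(1 + SDb²/6.55)) = 0.88 / 0.78 / 0.58 at SDb = 1 / 2.5 / 5.

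Simulation (2,000 trials per cell, Monte Carlo SE about 0.007), nominal 90% CI of the placebo LS mean:

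| Layout | SDb 1 | SDb 2.5 | SDb 5 |
|---|---|---|---|
| 6 subjects, 0 df, SEQUENCE kept | 0.89 | 0.79 | 0.59 |
| 6 subjects, SEQUENCE omitted | 0.91 | 0.91 | 0.90 |
| 6 subjects, 1 df, SEQUENCE kept | 0.92 | 0.89 | 0.85 |
| 9 subjects, 3 df, SEQUENCE kept | 0.92 | 0.91 | 0.90 |

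With one subject per sequence and SEQUENCE kept, the 25 mg-placebo difference is covered at 0.90. A separate simulation of that layout gave LS-mean coverage of 0.90 / 0.87 / 0.83 / 0.75 / 0.67 at SDb 0 / 1 / 2 / 3 / 4, with the difference again at 0.90. When the outcome was change and the subject level was shared with the predose value, LS-mean coverage stayed at 0.89 to 0.90.

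**How often.** Full aliasing is impossible with 7 or more subjects. For six it depends on an allocation the documents do not give: 8/84 = 9.5% of the six-subject subsets of 9 evenly allocated subjects, 6!/6⁶ = 1.5% for six unblocked subjects, and certain for six subjects forming one complete block.

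**The case for a change.** The case for an edit is that text and code should name one outcome, and the edit is cheap. The LS means and their CIs are named outputs, so their scale should not depend on a document the reader cannot see. A completer fit of six is also not far-fetched: the plan expects nine to fall to about six, and SAP 5.3.5 already asks for a completer summary. A rule based only on the sequence layout would be short.

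Much of this stands. The SAP does not define AVAL, and the aliasing is exact when its condition holds. But 5.5.2 already fixes the analysed variable as change and also has it summarized by treatment group, so mean changes are tabulated whatever AVAL holds. The listing in 13.2 is a template with a placeholder dataset name. A programmer would set the response from 5.5.2 and BASE from 8.1, or label the LS means as levels at mean baseline; either gives the same comparison.

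The aliasing argument reaches no committed analysis. Evaluable is a sample-size term in SAP 4, not an analysis set, and no mixed-model fit on six subjects is specified. The undercoverage needs a zero variance estimate, which was assumed and not run in SAS, and a sizeable between-subject SD remaining after adjustment for baseline. The 0.59 figure is extreme: SDb 5 with residual SD 2.56 gives a total SD of √(25 + 6.55) = 5.6, on a 0 to 14 scale where the largest possible SD at mean 8 is √(8 × 6) = 6.9. Dropping SEQUENCE would also depart from the model in Protocol 9.7.1.7.2 to protect single-arm means that are not the primary comparison.

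**Conclusion.** No change to the plan follows. The undefined AVAL is a gap in a code template that 5.5.2 and 8.1 let an analyst fill sensibly. At worst every LS mean is offset by mean BASE, while the dose-placebo differences and their 90% CIs are identical. It is enough that the dataset specification or table shell states the scale.

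The aliasing is real algebra in a fit the plan does not commit to. It cannot occur with 7 or more analysed subjects, and about 9 are planned. If someone refits the model on a subset with one subject per sequence, the CIs of the individual LS means should not be relied on and those of the differences can be.

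This rests on BASE following SAP 8.1 in both response and covariate, and on the PD Analysis Set holding at least 7 subjects. The coverage figures for the aliased case also assume the between-subject SDs shown and a reported subject variance of zero. The conclusion on the differences needs neither of those last two assumptions, because these contrasts are within-subject.
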